### 8.3 Secondary Efficacy Analyses

*Duration of response (DOR)* will be calculated for patients who achieve a CR or PR, and is defined as the time from the date of first documented response (CR or PR) to the date of documented progression or death of any cause after achieving response. Patients who discontinue the study without disease progression or death or patients with an event after 2 or more missing/inadequate disease assessment or patients with an event after the start date of alternate anti-cancer therapy will be censored at their last response assessment date or last assessment prior to the start date of alternate anti-cancer therapy, whichever is earlier. The number of events and the number of censored patients will be summarized, and the median time to PD or death event (reported in days), its 95% confidence interval, and the 25th and 75th percentiles on the time to event will be summarized using Brookmeyer-Crowley method.

*Disease Control Rate (DCR)* is defined as the percentage of patients who have achieved CR, PR, or SD lasting at least 4 weeks. DCR at any time during the study will be summarized, as per the RECIST assessment method.

*Progression Free Survival (PFS)* is defined as the time from the first PF-07901800 infusion (Cycle 1 Day 1) to PD or death of any cause, whichever is first. Patients without disease progression or death or patients with an event after 2 or more missing/inadequate disease assessment or patients with an event after the start date of alternate anti-cancer therapy will be censored at their last response assessment date or last assessment prior to the start date of alternate anti-cancer therapy, whichever is earlier.

The number of events and the number of censored patients will be summarized. PFS rate at selected times, as well as the median time to event (reported in days), its 95% confidence interval, and the 25th and 75th percentiles on the time to event will be summarized using Brookmeyer-Crowley method. Kaplan-Meier plot of PFS will also be provided.

*Overall Survival (OS)* is defined as the time from the first PF-07901800 infusion (Cycle 1 Day 1) to death of any cause. Patients last known to be alive will be censored at their last known alive date. Kaplan-Meier methodology similar to the PFS analysis will be used to summarize the results.

Pfizer Inc. / Protocol: TTI-621-03/C4961003  
IQVIA Biotech (Confidential) Project # YXA42460

*Duration of Disease Control (DDC)* is defined in patients who achieved a best overall response of SD or better, as the time from the first PF-07901800 infusion (Cycle 1 Day 1) to the date of documented progression or death of any cause, and will be calculated for patients who achieve a CR, PR or SD lasting at least 4 weeks. Patients without disease progression or death or patients with an event after 2 or more missing/inadequate disease assessment or patients with an event after the start date of alternate anti-cancer therapy will be censored at their last response assessment date or last assessment prior to the start date of alternate anti-cancer therapy, whichever is earlier. The number of events and the number of censored patients will be summarized, and the median time to PD or death event (reported in days), its 95% confidence interval, and the 25th and 75th percentiles on the time to event will be summarized using Brookmeyer-Crowley method.

*Time to progression (TTP)* is defined the same as PFS, except that death is not considered an event. Patients who die without PD or patients with PD after 2 or more missing/inadequate disease assessment or patients with PD after the start date of alternate anti-cancer therapy will be censored at their last disease assessment prior to the start date of alternate anti-cancer therapy, whichever is earlier. The number of events and the number of censored patients will be summarized. The median TTP (reported in days), its 95% confidence interval, and the 25th and 75th percentiles on the time to event will be summarized using Brookmeyer-Crowley method.

*Time to new lesion* is defined as the time from the first PF-07901800 infusion (Cycle 1 Day 1) to a new lesion appearance. Patients without new lesion or patients with new metastases after 2 or more missing/inadequate disease assessment or patients with new metastases after the start date of alternate anti-cancer therapy will be censored at their last response assessment date or last assessment prior to the start date of alternate anti-cancer therapy whichever is earlier. The number of events and the number of censored patients will be summarized. The median time to event (reported in days), its 95% confidence interval, and the 25th and 75th percentiles on the time to event will be summarized using Brookmeyer-Crowley method.

Waterfall plot for target lesion tumor response by individual will be presented, indicating best tumor response (maximum tumor reduction from baseline) at any time point for each subject. The plot will have one bar per subject sorted from worst to best response with color by dose administered. Tumor response will be calculated based on the type of cancer that the patient has, with the appropriate measure using RECIST.

Pfizer Inc. / Protocol: TTI-621-03/C4961003  
IQVIA Biotech (Confidential) Project # YXA42460

Swimmer plots for tumor response will be generated with RECIST assessment. The plots will have one horizontal bar per subject firstly sorted by Best Response, and then sorted from earliest to latest time to start of response for CR and PR; within categories of SD, PD and NE, patients will be sorted by maximum observation duration. Symbols within the swimmer plot will indicate time to start and end of each new level of response (if the end of one response is the start of a new type of response by definition, only the start will be shown). The plots will also show the length of treatment duration a patient had.

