**4.4. Secondary Endpoints**

- Overall safety profile as assessed by the type, frequency, severity, timing and causal relationship of any adverse events, changes in vital signs, ECGs, serum chemistry or other laboratory assessment, treatment delays or discontinuations for patients enrolled into the selected dose level cohorts in the expansion portion of the study
- Progression-free survival (PFS), overall survival (OS), disease control rate (DCR [CR + PR + SD]), duration of response (DOR), duration of disease control, time to progression and time to new metastases as defined by RECIST v1.1 criteria, time to worsening of ECOG performance status ([Appendix A](#)), time to worsening of patient-reporting outcomes assessments

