- j Assessed objectively by CT, MRI or PET/CT; the method used at baseline should be used for the duration of patient participation. Performed every  $6 \pm 1$  week for the first 18 weeks (during combination treatment), every  $8 \pm 1$  week until Week 50 or patient has been on study for one year, and every  $12 \pm 2$  weeks thereafter. CR or PR should be confirmed by repeat assessment at least four weeks after initial observation; treatment can continue during the interval between initial observation and confirmation. In the event that a patient is removed from the study in the absence of radiologic disease progression, a radiologic disease assessment should be performed at the Safety Follow-Up Visit if not performed within the previous four weeks and disease status should be assessed during Long-Term Follow-Up until radiologic demonstration of progression or initiation of new anti-cancer therapy, whichever occurs first
- k Patient-reported health-related quality of life will be assessed with the EORTC QLQ-C30 tool on Day 1 of every cycle and at the Safety Follow-Up visit prior to initiation of study treatment or other study activities

- i Doxorubicin should be administered through a free-flowing catheter at 75 mg/m^2 by intravenous infusion in less than 60 minutes. Prophylaxis against emesis and for prevention of febrile neutropenia should be administered as described in [Section 5.2.1.1](#); additional prophylaxis in accordance with institutional guidelines is acceptable
- m Cardioprotective administration of [dexrazoxane](#) should be initiated no later than initiation of Cycle 5 unless earlier initiation is medically advised or standard of care at a particular institution
- n Prophylaxis as described in [Section 5.2.1.2](#) will be initiated at least 30-60 minutes prior to initiation of TTI-621 infusion. TTI-621 is administered intravenously over 2 hours. At the Investigator's discretion and in the absence of infusion-related reaction in prior cycles, duration of infusion may be reduced to 60 minutes beginning with Cycle 2. Patients should be observed for one hour after infusion with vital signs assessment in 30-minutes for signs of infusion-related reaction in Cycle 1; the observation period may be reduced at the Investigator's discretion in patients who tolerate the infusion well and do not experience infusion-related reaction.

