**Cycle 8 Day 1**

- LVEF by transthoracic echocardiogram or MUGA (unless performed within previous 4 weeks)

***Safety Follow-Up Visit (30 + 5 days after last administration of study treatment or before initiation of subsequent anti-cancer therapy, whichever occurs soonest)***

- Patient-reported QoL assessment
- Complete physical examination
- Vital signs (temperature, blood pressure, pulse rate, respiratory rate, weight, pulse oximetry)
- LVEF by transthoracic echocardiogram or MUGA (unless performed within previous 4 weeks with no abnormalities)
- ECOG PS
- Serum chemistry (unless performed within previous 72 hours)
- Hematology (unless performed within previous 72 hours)
- 12-lead ECG
- Urine or serum pregnancy test (female patients of childbearing potential only)
- Radiologic assessment of disease status (unless performed within previous 7 days)
- Adverse events
- Concomitant medications and procedures
- Blood collection for CCI [REDACTED]

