**12.3.3. Clinical Benefit**

Clinical efficacy will be evaluated by tumor response for patients with measurable disease as assessed by the Investigators using RECIST v1.1 (Appendix B). Duration of response will be calculated for patients who achieve a CR or PR and is defined as the time from the date of first documented response (CR or

PR) to the date of documented progression or death after achieving response. Disease control rate is defined as the percentage of patients who have achieved CR, PR, or SD lasting at least 12 weeks.

Clinical activity based on CCI [REDACTED] will be assessed as an CCI [REDACTED] of the study.

Patients enrolled in an expansion cohort who withdraw from the study prior to the first objective disease assessment for a reason other than disease progression or safety will be replaced in order to meet the statistical criteria for the Simon two-stage design; these patients will not be included in the response-evaluable population. For a patient enrolled into the dose expansion portion of the study based on local pathology that is not confirmed during central review, the patient must be replaced for purposes of meeting the statistical requirements of the study but may be allowed to continue on treatment after discussion with the Sponsor Medical Monitor.

For patients with asymptomatic progression only or suspected pseudoprogression, the patient may continue treatment beyond progression until a confirmation scan at least four weeks later has confirmed progression.

Efficacy analyses will be based on the efficacy analysis population, i.e. all patients who received at least one dose of study treatment, unless otherwise specified.

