When no imaging/measurement is done at all at a particular time point, the patient is not evaluable (NE) at that time point. If only a subset of lesion measurements are made at an assessment, usually the case is also considered NE at that time point, unless a convincing argument can be made that the contribution of the individual missing lesion(s) would not change the assigned time point response, which is most likely to occur in the case of PD; e.g, if only 2 of 3 baseline target lesions are assessed and result in a > 20% increase in the sum, then the patient would be assessed as a PD regardless of the missing lesion.

Patients with a global deterioration of health status requiring discontinuation of treatment without objective evidence of disease progression at that time should be classified as having symptomatic deterioration. Every effort should be made to document the objective progression, even after discontinuation of treatment.

In some circumstances, it may be difficult to distinguish residual disease from normal tissue. When the evaluation of CR depends on this determination, it is recommended that the residual lesion be investigated (fine needle aspiration/biopsy) before confirming the CR status.

*Confirmatory Measurement/Duration of Response*Confirmation

Radiographic tumor assessments are required. If an initial CR or PR is noted, confirmatory scans must be performed at least 4 weeks later. In the case of SD, follow-up measurements must have met the SD criteria at least once after study entry at a minimum interval of no less than 4 weeks.

Duration of Overall Response

The duration of overall response is measured from the time measurement criteria are met for CR or PR (whichever is first recorded) until the first date that recurrent or PD is objectively documented (taking as reference for PD the smallest measurements recorded since the treatment started).

[figure not shown]
The duration of overall CR is measured from the time measurement criteria are first met for CR until the first date that recurrent disease is objectively documented.

Duration of Stable Disease

Stable disease is measured from the start of the treatment until the criteria for progression are met, taking as reference the smallest measurements recorded since the treatment started.

Reference: Eisenhauer EA, Therasse P, Bogaerts J et al. New response evaluation criteria in solid tumours: revised RECIST guideline (version 1.1). Eur J Cancer 2009; 45:228-247.

CCI

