## 1.2 Protocol and Amendment History

This Statistical Analysis Plan (SAP) is based on version 2.0 of Protocol TTI-621-03 (17JUN2022). This SAP will govern the analysis of data from this study. The plan for efficacy analyses may be modified prior to the clinical database lock. Any deviations from the analysis plan, will be documented as such in the clinical study report.

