Best overall response (BOR) will be assessed based on reported overall lesion responses at different evaluation time points from the date of first study treatment until the first documentation of PD, according to the following rules. Only tumor assessments performed on or before the start date of any subsequent anti-cancer therapies (from the "Survival Status" eCRF) will be considered in the assessment of BOR. Clinical deterioration will not be considered as documentation of disease progression.

BOR based on confirmed responses (primary definition):

*Best Overall Response (BOR)* is defined as the best response recorded (CR, PR, SD, PD, NE per RECIST) from the start of the treatment until disease progression, taking as reference for PD the smallest measurements recorded since the treatment started. The patient's best response assignment will depend on the achievement of both measurement and confirmation criteria.

The tumor responses are required to be confirmed by radiographic tumor assessments. If an initial CR or PR is noted, confirmatory scans must be performed at least 4 weeks later. In the case of SD, follow-up measurements must have met the SD criteria at least once after study entry at a minimum interval of no less than 4 weeks.

Pfizer Inc. / Protocol: TTI-621-03/C4961003  
IQVIA Biotech (Confidential) Project # YXA42460

- CR = at least two determinations of CR at least 4 weeks apart and before first documentation of PD.
- PR = at least two determinations of PR or better (PR followed by PR or PR followed by CR) at least 4 weeks apart and before first documentation of PD (and not qualifying for a CR).
- SD (applicable only to patients with measurable disease at baseline) = at least one SD assessment (or better)  $\geq 4$  weeks after the date of first study treatment and before first documentation of PD (and not qualifying for CR or PR).
- Non-CR/non-PD (applicable only to patients with non-measurable disease at baseline) = at least one non-CR/non-PD assessment (or better)  $\geq 4$  weeks after the date of first study treatment and before first documentation of PD (and not qualifying for CR or PR).
- PD = first documentation of PD  $\leq 12$  weeks after the date of first study treatment (and not qualifying for CR, PR, SD or non-CR/non-PD4)
- NE: all other cases.

Objective Response (OR) is defined as confirmed BOR of CR or PR according to RECIST v1.1. OR rate (ORR) is the proportion of patients with OR in the analysis set.

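### The SAP counts stable disease of 4 weeks towards the disease control rate where the protocol requires 12 weeks, and its visible text does not record the change

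*SAP*

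**What the plan says.** Protocol 12.3.3 gives the definition: "Disease control rate is defined as the percentage of patients who have achieved CR, PR, or SD lasting at least 12 weeks". SAP 8.3 uses nearly the same sentence with a different number; DCR "is defined as the percentage of patients who have achieved CR, PR, or SD lasting at least 4 weeks". SAP 1.2 states: "This Statistical Analysis Plan (SAP) is based on version 2.0 of Protocol TTI-621-03 (17JUN2022", which is the version containing the 12-week rule.

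The endpoint lists do not settle the matter. Protocol 4.4 has "disease control rate (DCR [CR + PR + SD" with no duration, and SAP 3.2 does the same.

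Three other provisions bear on the point:

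- **Minimum for a best response of SD.** SAP 8.1 says follow-up measurements "must have met the SD criteria at least once after study entry at a minimum interval of no less than 4 weeks". Its bulleted rule counts the 4 weeks from first study treatment. Protocol Appendix B has the same minimum.
- **How long SD lasts.** Protocol Appendix B, Duration of Stable Disease: "Stable disease is measured from the start of the treatment until the criteria for progression are met".
- **Scan times.** Protocol Table 24, footnote j, sets radiologic assessment every 6 ± 1 weeks "for the first 18 weeks (during combination treatment").

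**The concern.** The two documents give different definitions of one named endpoint, and the looser one will be programmed. A reader holding the protocol would take a reported DCR to mean control for at least 12 weeks. The SAP's version asks for no durability beyond what is needed to be called SD at all.

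The visible SAP has no section on changes from the protocol. SAP 1.2 undertakes to document deviations from the SAP in the study report, which does not cover a departure of the SAP itself from the protocol.

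At stake is the meaning and possibly the size of one descriptive secondary result, for which Protocol 12.4 plans a 95% confidence interval.

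**Working it through.** The documents give no expected rate or power for DCR, so there is no stated figure to reproduce. The check is a comparison of rules, followed by an illustration of size.

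**Step 1. What the 4-week limit adds.** The first routine scan falls at 6 ± 1 weeks, i.e. days 35 to 49, which is already past day 28. A scan before day 28 would have to be off schedule, for example at a Safety Follow-Up Visit held 30 days after the last dose "or before initiation of subsequent anti-cancer therapy, whichever occurs soonest" (Protocol Section 11). SAP 8.1 does not accept SD seen only at such a scan as a best response. The limit in SAP 8.3 therefore removes essentially no one, and DCR becomes the proportion with a best response of SD or better.

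**Step 2. Direction.** SD lasting 12 weeks (84 days) also lasts 4 weeks, and CR and PR count under both rules. So, on the same patients, SAP DCR ≥ protocol DCR.

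**Step 3. Example patients.** Days are counted from first dose.

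| Scan results | SD duration (Appendix B) | SAP | Protocol |
|---|---|---|---|
| SD day 42, PD day 77 | 77 days, under 84 | counts | does not count |
| SD day 42, PD day 84 | 84 days | counts | counts |

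Day 77 lies inside the second scan window (12 ± 1 weeks, days 77 to 91). Under the Appendix B clock, the definitions separate patients with a single qualifying SD scan only when PD is documented before day 84.

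**Step 4. Illustration of size.** Inputs:

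- Median PFS *m* = 3, 4 or 5 months. The protocol synopsis cites PFS of 3–5 months for doxorubicin alone; treating these as medians is an assumption.
- Exponential PFS (assumption): S(d) = exp(−ln 2 × d / (30.4375 m)).
- First scan d1 uniform on days 35–49 and second scan d2 uniform on days 77–91, 15 whole days each (assumption).

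A patient counts under the SAP only if progression-free at d1, progressed by d2, and d2 < 84. The days 77–83 are 7 of 15, so

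gap = (7/15) × [mean S(d1) − mean S(d2) over days 77–83].

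SAP 6.8 computes durations as stop minus start plus 1. PD found 83 days after first dose then already gives 84 days, leaving days 77–82 (6 of 15):

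gap = (6/15) × [mean S(d1) − mean S(d2) over days 77–82].

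| Median | Without the +1 day | With the +1 day |
|---|---|---|
| 3 months | (7/15)(0.727 − 0.545) = 8.5 points | (6/15)(0.727 − 0.547) = 7.2 points |
| 4 months | (7/15)(0.788 − 0.634) = 7.2 points | (6/15)(0.788 − 0.636) = 6.1 points |
| 5 months | (7/15)(0.826 − 0.695) = 6.1 points | (6/15)(0.826 − 0.696) = 5.2 points |

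For a 31-patient cohort this is 31 × 0.052 = 1.6 to 31 × 0.085 = 2.6 patients. With an assumed 8-month median the gaps are 4.2 and 3.6 points. If every second scan falls at day 84 or later, the gap is zero.

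Not modelled: cycle delays that move scans, deaths, PD found at unscheduled scans, and patients with one SD scan and no later scan.

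**The case against.** **The 4-week figure has a source in the protocol.** The endpoint list ties DCR to RECIST v1.1, and Appendix B sets a 4-week SD minimum. This may well be where the SAP's number came from. It does not remove the conflict: Appendix B governs when SD may be assigned as a best response, while 12.3.3 says how long SD must last to count as disease control. The two rules can stand together. That the SAP's limit repeats its own best-response minimum is a redundancy, not a second defect.

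**The effect may be small or nil.** This stands. Under the Appendix B clock it depends on how many second scans fall before day 84.

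**The consequence is limited.** This also stands. DCR is descriptive and no decision rule uses it. Early progression remains visible in the planned PFS summaries and swimmer plots.

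**The SAP states 4 weeks openly.** True. Table shells are not among the documents, so it cannot be said that the output would carry no label. Some SAP front pages were removed and Section 11 is redacted, so the claim is only that the visible text records no change.

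**Stronger readings that the documents do not support.** A reader might infer that the end of the SD clock is undefined; Appendix B gives both ends. A reader might also compare progression-free proportions at days 42 and 84, which under the same model gives 14 to 20 points, or time SD to the last SD scan, which gives 20 to 34 points depending on scan timing. The first requires SD to be seen on a scan at day 84, and the second stops the clock before progression. Neither is the protocol's rule.

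**Conclusion.** The conflict is real and rests on the text alone: 12 weeks in Protocol 12.3.3 against 4 weeks in SAP 8.3, in a SAP that says it follows that protocol version. As written, the SAP reports a best response of SD or better under the name DCR, and the result is equal to or higher than the protocol's on the same patients.

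The size cannot be derived from the documents. On the protocol's SD clock the illustration gives zero if second scans fall at day 84 or later, and about 5 to 9 points if scans are spread evenly over their windows. It assumes exponential PFS at doxorubicin-alone medians of 3 to 5 months, which may not fit the combination, and it is not an upper bound.

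It would be wrong to infer that the trial's main conclusion is affected. The objective response rate and the Simon two-stage rule do not use DCR. The SAP should be corrected because a reported secondary endpoint would otherwise not be the one the protocol defines.

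**What to change.** - In SAP 8.3, define DCR with SD of at least 12 weeks, as in Protocol 12.3.3, and state that SD duration is timed as in Protocol Appendix B. Say whether the plus-one-day convention of SAP 6.8 applies to the 12 weeks.
- If the 4-week version is kept, report it as a separately labelled supplementary analysis and record it as a departure from the protocol.
- State whether the Duration of Disease Control population in SAP 8.3 keeps its 4-week minimum. The protocol sets no minimum for that endpoint, so either choice is open, but disease control should not carry two unlabelled meanings in one section.

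The cost is SAP wording and a re-derivation of DCR from scans already collected. No new data or change of sample size is needed. The reported DCR stays the same or falls.
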